Studies in adults have repeatedly demonstrated that treatment of clinically-defined acute sinusitis with conventional doses of amoxicillin (Williamson, et al, 2007; Garbutt et al., 2012,), and even of amoxicillin/clavulanate (Wald et al, 1986; Bucher et al., 2003) provide little or no clinically significant benefit. How to account for the negative results?

First, antibiotics may not be useful, i.e. the persistence of symptoms may be a part of the natural history of acute sinusitis, and the patients' immune systems are adequate to eradicate the bacteria. This is the conclusion, for example, of Garbutt and colleagues (2012).

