2003). One reason for the questionable value of amoxicillin/clavulanate may be that clavulanate has been shown (Dinis et al, 2000) to have uneven penetration into sinus tissue (and would likely, therefore, to have at least as uneven penetration into sinus fluid). Moreover, the impact of adding clavulanate is diminished, as acknowledged by the IDSA, by the presence, in a variable proportion of patients, of penicillin-resistant S. pneumoniae (as well as methicillin-resistant S. aureus); it is for this reason that the IDSA recommends high-dose amoxicillin/clavulanate when the rate of penicillin-resistant S pneumoniae exceeds 10%. Indeed, the superior effectiveness of high dose was suggested by a small retrospective study in which the number of resistant S. pneumoniae in nasopharygeal swabs was reduced from 8 cases before treatment to 5 cases after treatment with 1.5 grams per day of amoxicillin with clavulanate but from 8 cases to only 1 case after treatment with 4.0 grams day of amoxicillin with clavulanate (Brook et al., 2005).

Third, studies could have been falsely negative if the methods used to measure the effect underestimated it. Garbutt et al (2012) used the mean response to the 16 questions of the SNOT-16 as the primary outcome. Is it possible that the responses to the truly meaningful questions (e.g. fatigue) were diluted by responses to questions that are less important to the patient or do not change very fast (e.g. runny nose) or are not much affected by antibiotics (e.g. sneezing)? In support of its validity as a measure of treatment effect, however, the SNOT-16 was validated by another group (Quadri et al, 2013), and the question on subjective improvement also showed no significant difference at day 3 (37% of amoxicillin group vs 34% of placebo group reported that symptoms were a lot better or absent), although at day 7 there was a significant increase in subjective improvement in the antibiotic group (74% vs 56%, p=.02).

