The purpose of the study is, using study procedures duplicating in large part those of Garbutt et al (2012), to compare the benefits of 2 treatment arms—high-dose amoxicillin/clavulanate (2000 mg amoxicillin/125 mg po bid) vs regular-dose amoxicillin/clavulanate (875 mg amoxicillin/125 mg po bid)--at day 3 (primary endpoint) and day 10 (secondary endpoint), by reported degree of improvement (primary endpoint, as in Wald et al., 2009) and by SNOT-16 (secondary endpoint, but which was the primary endpoint in Garbutt et al, 2012). We will use amoxicillin/clavulanate, rather than amoxicillin alone, to be in accord with the IDSA 2012 guideline (IDSA, 2012). The duration will be 7 days in line with the IDSA guidelines. We will not have a pure placebo arm since 1) the IDSA guidelines recommend treatment; 2) clinical studies (Wald et al, 1986; Bucher et al., 2003) suggest that treating with the IDSA-recommended regular-dose amoxicillin/clavulanate is equivalent, or almost equivalent, to giving a placebo; 3) we will not exclude patients who we would not want to risk giving a true placebo; and 4) we know that, because of patients' continued belief in the efficacy of antibiotics, recruitment will be easily in a study with two treatment arms, rather than treatment and placebo arms. In addition, we will study whether the response to antibiotics can be predicted by the presence or not of penicillin-resistant S. pneumoniae in the nasopharynx.

Thus the study questions are: 1. Is high-dose amoxicillin/clavulanate superior to regulardose in improving the clinical symptoms of presumed sinusitis? 2. Does the higher dose result in increased incidence and/or severity of adverse effects, such as diarrhea? 3. Does the resistance pattern of S. pneumonia in nasopharyngeal cultures predict response to antibiotic treatment? The hypotheses are yes for #1, no for #2, and no for #3 (but with the expectation of insufficient power to answer question #3).

B. Study Design

Study type: randomized, double-blind clinical study with two active treatment arms

Location: AMC Internal Medicine and Pediatrics office in Latham, NY

Duration: 2 years; each participant will be in the study for 30 days.

Subjects:

Inclusion criteria

1. Adults age 18 and over. The study on children already indicates a benefit of high-dose amoxicillin-clavulanate over placebo. The restriction to adults eliminates the need for parental consent.

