- 2. Presenting with symptoms consistent with acute sinusitis according to standard guidelines. Garbutt et al, 2012, used: a) history of maxillary pain or tenderness in the face or teeth, purulent nasal secretions, and rhinosinusitis symptoms for 7-28 days that were not improving or were worsening, or b) rhinosinusitis symptoms for <7 days that had significantly worsened after initial improvement. The IDSA's 2012 guidelines are slightly different and will be used here:
 - a. Persistent symptoms (as above) and not improving (lasting for > 10 days); or
 - b. Severe symptoms or signs of fever ≥ 102 degrees F and nasal discharge or facial pain (lasting for > 3-4 days); or
 - c. Worsening symptoms or signs characterized by a new onset of fever, headache, or increase in nasal discharge following a typical viral URI that lasted 5-6 days and was initially improving ("double-sickening").
- 3. Both the treating physician and the patient must think that antibiotic treatment, if it helped, would be indicated.

Exclusion criteria

- 1. Peviously enrolled in the study
- 2. Allergic or intolerant to amoxicillin, amoxicillin/clavulanate, ampicillin, or penicillin, or severe reaction to any other beta lactam.
- 3. Lactation, since no data on clavunlanate. Note that pregnancy is not exclusion since amoxicillin/clavulanate is category B.
- 4. Taking allopurinol since it increases substantially the risk of rash.
- 5. Cognitively unable to give informed consent and/or to provide accurate assessment of own symptoms (as assessed by the person obtaining consent).
- 6. Chronic or recurrent "sinus" problems. Defined as persistent symptoms of "sinus" congestion, not attributed to nasal allergies, for 8 weeks or more (Mayo Cinic, 2014) or 2 or more episodes of antibiotic-treated "sinusitis" in past 3 months. These patients are at risk of anatomical or immunological abnormalities and of harboring antibiotic resistant organisms.
- 7. Need to start high-dose amoxicillin/clavulanate, doxycycline, or levofloxacin (i.e. the clinician's judgment that regular-dose amoxicillin/clavulanate would be unwise).
 - a. Signs of severe infection (e.g. evidence of systemic toxicity with fever $\geq 102 \text{ F}$)
 - b. Amoxicillin or penicillin within the past month (not, as in the IDSA guidelines [2012], any antibiotics)
 - c. Immunocompromised

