Note that, unlike the IDSA guidelines, (2012) we do not plan automatically to treat with high-dose amoxicillin/clavunate all patients >65 or those who were hospitalized recently but not treated with antibiotics.

- 8. Suspicion of MRSA.
- 9. Drug warnings
 - a. Chronic kidney disease with estimated GFR < 30;
 - b. Hepatic impairment (not including isolated transaminase elevation <2 times normal);
 - c. Current mononucleosis (because of amoxicillin-induced rash);
 - d. History of antibiotic-associated colitis.
- 10. Need to hospitalize because of severity of infection, respiratory distress, or vulnerability of patient.

Treatment arms

- 1. Amoxicillin/clavulanate 1000/62.5 ER 2 tabs po bid for 7 days. (total pill burden 4 per day)
- 2. Amoxicillin/clavulanate 875/125 tabs 1 tab + 1 placebo tab po bid for 7 days (total pill burden 4 per day).

The duration of 7 days is in accordance with IDSA guidelines.

Both groups would be advised: 1) to instill saline into each nostril at least 2 times a day (1/4 tsp salt dissolved in 4 oz of distilled or boiled water, 1 teaspoonful administered into each nostril by sniffing, by syringe, or by Neti-pot; 2) to take acetaminophen for discomfort (not to exceed a total daily dose of 3 grams, or 2 grams if the patient drinks ETOH).

The pharmacist would prepare the medication bottles and randomize them (i.e., number the two sets of medication bottles as determined by a random number generator and keep the list of correlations between bottle number and actual contents).

Measurements (clinical)

- 1. Diagnostic criteria for acute sinusitis (as listed above): clinician to record these (including duration of illness and the category of acute sinusitis)
- 2. Initial additional data collection by nurse or clinician: previous side effects with antibiotics, antibiotics within past month, hospitalization in past 5 days, comorbidities (e.g., diabetes, heart disease, and lung disease)
- 3. Sinonasal Outcome Test-16 (SNOT-16) at days 0, 3, 10, and 30 (for validation of the form, see Garbutt et al, 2011, and Quadri et al, 2013).
- 4. Patients' summary assessment of their condition at days 3, 10, and 30: a lot worse, a little worse, the same, a little better, a lot better, no symptoms (as used by Garbutt et al, 2012).
- 5. Side effects at days 3 and 10
 - a. Diarrhea: none, mild, moderate, severe
 - b. Allergic reaction: rash without itching, rash with itching or hives
 - c. Other: abdominal pain, vaginal discharge and itching, other

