 - f. The impact of other clinical characteristics on the outcomes: age, sex, comorbidities, sinusitis category.

3. Secondary culture endpoints

- a. The proportion of participants with S. pneumoniae on NP culture and the proportion of these with moderate and high resistance to penicillin
- b. The proportion of participants with moderately or highly resistant S penumoniae versus the others who achieve the primary and secondary clinical end points

4. Other questions

- a. What percentages were treated without meeting IDSA criteria; were excluded; and refused to participate?
- b. How frequently did participants guess correctly which medication they were taking, and were their guesses associated with outcomes?
- c. How did the change in SNOT-16 score—and individual questions—correlate with holistic ratings of improvement?
- d. How many patients had MRSA, and did carriage of MRSA affect outcomes?

Sample size determination

1. For improvement in symptoms at day 3: Garbutt et al, 2012, has 34% symptom improvement in controls (placebo); if a clinically meaningful impact of high-dose amoxicillin-clavulanate is to increase the response rate to 50% (giving a NNT of 7), 146 patients in each group would be required to have an 80% power to detect this difference (if it exists), with alpha .05 (http://www.sealedenvelope.com/power/binary-superiority/).

- The statistical consultant calculates, with alpha .05 only one-sided (not inappropriate since we are interested only in improvement), the needed sample would be 120 in each group.
- 2. For change in SNOT score: Garbutt et al, 2012 calculated that 100 patients in each group were needed to detect a true difference of .25. To detect the "clinically meaningful difference" of .50, fewer would be needed.

We propose, therefore, to aim for 150 patients in each group, i.e. a total of at least 300 participants in Med-Ped over a 2 year period.

In our patient population of over 10,000, we see about 10 patients a week with presumed acute sinusitis during the non-summer months—a total of over 600 last year with a diagnostic code of acute sinusitis--so we expect no problem in reaching our recruitment goal.

Procedure

Prior to enrollment

- 1. All clinicians achieve up-to-date certification in research ethics. Only those who are certified will enroll patients.
- 2. PI trains all the nurses and clinicians to be able to explain the study to patients, collect study data, and obtain informed consent.

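### Does sizing an active-controlled trial on a 34% placebo response rate undermine the stated 80% power?

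*Combined protocol and SAP*

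**What the plan says.** Under B. Study Design, Sample size determination, the control rate is "34% symptom improvement in controls (placebo" and the meaningful effect is "to increase the response rate to 50% (giving a NNT of 7". The same sentence says that 146 patients per group give 80% power to detect that difference at alpha .05. A one-sided variant needs 120 per group, and the plan settles on 150 per group, 300 in all.

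The control arm, under Treatment arms, is "Amoxicillin/clavulanate 875/125 tabs 1 tab + 1 placebo tab po bid for 7 days". There is no pure placebo arm. One reason given under Purpose of Current Study is that earlier clinical studies suggest regular-dose amoxicillin/clavulanate "is equivalent, or almost equivalent, to giving a placebo". The background opens on the same theme: conventional doses "provide little or no clinically significant benefit" in adults. It also gives the day-3 result of the trial that supplies the 34%: "37% of amoxicillin group vs 34% of placebo group reported that symptoms were a lot better or absent", reported as not significantly different.

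**The concern.** A trial with an active control is normally sized on the response expected under that control. Here the rate comes from a placebo arm, although the protocol itself quotes the antibiotic arm of the same trial, on the same day and the same response categories, at 37%. The sample-size section neither refers back to the near-equivalence premise nor shows power at any other control rate. It also describes the target in two ways, as a 50% response rate and as an NNT. These agree when the control rate is 34% but separate if it moves.

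The planned size has little slack in the two-sided calculation. If the control rate were a few points higher and the target were held at 50%, power would fall well below 80%, and a null result would be harder to interpret.

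**Working it through.** **Inputs.** Control 34% and target 50%, two-sided alpha .05, 80% power, 150 per group (Sample size determination). The test is a chi-square (D. Data Analysis, where alpha is printed as .05%, read here as .05). The 37% comes from the background. All powers assume 150 patients per group with a day-3 result.

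**Reproducing the plan's figure.** With the unpooled normal formula,

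n = (1.960 + 0.842)² × [p₁(1 − p₁) + p₂(1 − p₂)] / (p₂ − p₁)²

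= 7.849 × (0.2244 + 0.2500) / 0.16² = 145.4, rounded up to 146 per group. This matches the plan. The pooled formula gives 149. The NNT also agrees: 1/0.16 = 6.25, rounded up to 7.

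**Power at 150 per group.** The normal approximation is Φ[(p₂ − p₁)/SE − 1.960], with SE = √{[p₁(1 − p₁) + p₂(1 − p₂)]/150}:

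- 34% v 50%: SE 0.0562; Φ(0.885) = 81.2%
- 37% v 50%: SE 0.0568; Φ(0.331) = 63.0%
- 37% v 53%: SE 0.0567; Φ(0.862) = 80.6%

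Exact power of the uncorrected chi-square, by enumerating both binomials:

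| Control | Target | Difference | Power |
|---|---|---|---|
| 32% | 50% | 18 points | 89% |
| 34% | 50% | 16 points | 81% |
| 35% | 50% | 15 points | 76% |
| 36% | 50% | 14 points | 70% |
| 37% | 50% | 13 points | 64% |
| 37% | 53% | 16 points | 81% |

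Only 34% and 37% are control rates quoted in the protocol; 32%, 35% and 36% are illustrative. The pooled normal approximation gives 62.3% for 37% v 50%, so the methods span 62% to 64%.

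**What drives the drop.** Comparing 37% v 50% with 37% v 53% shows that the control rate itself hardly matters. Power falls because the assumed effect shrinks from 16 to 13 points. With the 16 points kept, power stays at about 81%.

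**How firm is 37%?** The background gives 166 participants for the earlier trial. Assuming about 83 per arm (the documents do not give arm sizes), the standard error of the difference is √(0.37 × 0.63/83 + 0.34 × 0.66/83) = 0.074. The observed 3 points are 0.03/0.074 = 0.4 standard errors.

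**The case for a change.** The strongest case for a change is that almost equivalent is not the same as equivalent. Three points on the control rate cost about 17 points of power against a fixed 50%, and a non-significant 37% v 34% does not show that the rates are equal. The near-equivalence premise is offered as a reason for omitting a placebo arm, not as the basis for the power. The phrase "increase the response rate to 50% (giving a NNT of 7" can be read as naming a rate, and 37% v 50% would be an NNT of 1/0.13 = 7.7, hence 8. A few added sentences would remove the doubt at almost no cost.

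The sensitivity is real and the arithmetic stands. But making 37% the planning rate would not clearly be an improvement. It is for amoxicillin alone, and the earlier trial had different entry criteria: for this trial the IDSA "guidelines are slightly different and will be used here". The documents give no day-3 rate for regular-dose amoxicillin/clavulanate. Nor do they bound the rate below at 34%. The background says earlier studies excluded the sickest patients, whereas this protocol says it will not exclude those it would not want to give a true placebo, so a lower control rate is also possible. Showing only higher rates would overstate the risk. As to the target, an NNT is itself a measure of difference, and the sentence goes on to state power for the difference.

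**Conclusion.** The concern does not call for a change. The sample size is reproduced exactly, the source of the 34% is labelled openly as placebo, and its use follows from a premise stated elsewhere in the same protocol. For the 16-point difference that the sentence powers, 150 per group gives about 81% whether the control rate is 34% or 37%. The 64% arises only if the control rate is 37% and the target is also held at 50%, that is, for a smaller effect than the one planned.

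A cross-reference to the premise, an explicit statement that the target is a 16-point difference, and power shown on both sides of 34% would make the section easier to read. These are optional. They would document a disclosed assumption without altering the 300 participants, the chi-square test, the day-3 endpoint or any conclusion. This judgement rests on reading the target as a difference and on full day-3 data at 150 per group; the 0.4 standard errors also assumes about 83 per arm in the earlier trial.

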- 3. Posters about the study are put in the waiting room and in the examining rooms.
- 4. The pharmacist prepares and numbers a set of medication bottles with either standard or high dose amoxicillin/clavulanate based on random number generation. Each bottle will include a label with dosing directions. A study allocation list will be kept by the pharmacist in a secure place in the office. The medication bottles and a log sheet to record medication #, patient name, and date will be kept in the locked medication room.

Enrollment

- 5. The nurse gives every patient with respiratory symptoms a SNOT-16 form to fill out and a handout about the sinusitis study (the same text that is posted in the waiting room and the examining rooms.) The nurse helps the patient to fill out the SNOT-16.
- 6. The clinician then assesses every patient with respiratory symptoms for suitability for the study, i.e., determines if the patient has acute sinusitis and is eligible for study, using the standard diagnostic criteria and considering the inclusion and exclusion criteria (marking them on the Data Collection Form).
- 7. The clinician indicates the disposition of each patient treated for acute sinusitis: meets criteria for inclusion, but not asked to participate (e.g., lack of time); treated even though not meeting IDSA criteria for acute sinusitis; presence of exclusion criterion; meeting all criteria but declined to participate; or entered into the study.
- 8. The clinician or nurse explains the study based on the Enrollment Script; the clinician obtains informed consent; and the clinician or nurse makes a copy of the consent form to give to the patient.
- 9. The clinician or the nurse obtains a nasal culture. If the patient prefers, he or she can insert the swab (under supervision to make sure it goes to mid nasal passage).
- 10. The clinician or nurse obtains the already-randomized medication bottle, writes the patient's name and date on the log sheet or (preferred) attaches a patient sticker, and writes the patient's number on the informed consent and on the culturette. The clinician gives the bottle of medication to the patient.

- 11. The patient is told that one tab has regular amoxicillin with clavulanate, the other tab has either a different formulation of amoxicillin with clavulanate or else an inactive ingredient (so that patients are not surprised if the pills look slightly different).

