 - a. To have the patient remain in the study, after reassurance and/or advice on treating side effects;
 - b. To switch the patient to a different antibiotic because of apparent inefficacy or bad side effects (and drop her out of active part of study):
 - c. To bring the patient into the office to be seen (and decide then if the patient will stay in or drop out of the study); or
 - d. To send the patient to the ED (if quite ill) (and drop her out of the active part of the study).
- 20. If the participant drops out, the clinician can ask the pharmacists to look up the results of the culture (if done) to help guide further management. In practice, this is highly unlikely

- since the patient who fails the study medication will be switched to another antibiotic (generally doxycycline or levofloxacin).
- 21. If a patient drops out, the clinician involved will fill out the Drop-Out form.
- 22. The participant who drops out of the active part of the study will still be called at 3, 10, and 30 days, if he or she agrees (to enable an intention to treat analysis with maximum data).
- 23. Culture results, identified only by the participant's study number, will be collected by the pharmacist and kept separately. The results will be entered onto the Data Collection Form and the data base only at the end of the study, i.e. will not be known to the residents and students as they make phone calls. The pharmacist will tell a clinician the results for a particular patient only if the patient drops out and knowledge of the culture result might help in further management.
- 24. At the end of the study, the Data Collection Forms for each participant will be scanned into the EHR (so that the data will be clinically useful for the patient) and then destroyed (along with the Day 0 SNOT-16 form).

Costs

1. Medication

- a. Amox-clav 1000/62.5 two tabs bid x 7 days = \$72.36 per patient. Total for 150 patents \$10,854. We will try to get the antibiotic from 2 different generic manufacturers so that the 2 tabs look slightly different. Thus the total cost may be higher, but unlikely more than \$12,000.
- b. Amox-clav 875/125 t tab bid x 7 days = \$7.00 per patient. Total for 150 patients \$1,050.
- c. Placebo. We are still trying to find information on costs, but doubt it will cost more than \$5 per pill. Total for 150 patients \$750 (or less).
- d. Packaging. Each patient will need 2 bottles and labels, likely \$1 per patient. Total for 300 patients of \$300.

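### What every patient is to be told about the two tablets is not true of the high-dose arm, and the plan for how that arm's tablets look is only an intention under Costs

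*Combined protocol and SAP*

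**What the plan says.** The trial is described as double-blind with two active arms. The Treatment arms section defines them as follows:

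- Arm 1 (high dose): "Amoxicillin/clavulanate 1000/62.5 ER 2 tabs po bid for 7 days".
- Arm 2 (regular dose): "Amoxicillin/clavulanate 875/125 tabs 1 tab + 1 placebo tab po bid for 7 days".

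The Purpose of Current Study section attaches the word 'regular' to the second of these: "regular-dose amoxicillin/clavulanate (875 mg amoxicillin/125 mg po bid".

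Procedure, Enrollment, item 11 then gives one statement for all patients, with no condition by arm: "one tab has regular amoxicillin with clavulanate, the other tab has either a different formulation of amoxicillin with clavulanate or else an inactive ingredient". Its stated aim is "so that patients are not surprised if the pills look slightly different". Item 8 of the same list says "The clinician or nurse explains the study based on the Enrollment Script"; that script is not in the available text, and neither is the consent form.

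The appearance of the high-dose tablets is addressed only under Costs, item 1a: "We will try to get the antibiotic from 2 different generic manufacturers so that the 2 tabs look slightly different". The same item adds "Thus the total cost may be higher, but unlikely more than" $12,000.

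The primary endpoint (Endpoints, item 1) is the patient's own rating of improvement, 48 to 72 hours after starting treatment. A treatment guess is collected at day 10 (Measurements (clinical), item 7a), and its relation to outcome is listed as a further question (Endpoints, item 4b).

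**The concern.** There are two linked problems. First, the statement that staff are directed to make describes one arm correctly and the other incorrectly. Second, the sourcing plan that would make the high-dose tablets look unlike each other is an intention in a budget line. The available text of the Treatment arms section, the pharmacist's preparation step (Enrollment list, item 4) and the rest of the Procedure sets no appearance requirement and no fallback.

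The blind is at stake. A high-dose patient who has been told that the two tablets differ in content, and who then finds two that look the same, has information that a regular-dose patient may not have. It is present from the first dose, before the day-3 rating. The planned chi-square test compares two proportions and cannot separate a shift caused by expectation from a shift caused by dose. The day-10 guess cannot repair this. It comes after the primary endpoint, and the protocol itself expects faster improvers to guess the higher dose, so the guess is confounded with response.

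**Working it through.** **Step 1. What the high-dose tablets are.** Inputs: 1000/62.5 mg per tablet, two tablets per dose (Treatment arms); high dose stated as 2000/125 mg twice daily (Purpose of Current Study).

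- Amoxicillin: 2 × 1000 = 2000 mg.
- Clavulanate: 2 × 62.5 = 125 mg.

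This reproduces the stated dose exactly, so both tablets are the ER product. If one of them were the 875/125 tablet, the other would have to supply 2000 − 875 = 1125 mg of amoxicillin and 125 − 125 = 0 mg of clavulanate. The documents mention no such product.

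**Step 2. Item 11 against each arm.**

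| Part of the statement | Arm 2 (875/125 + placebo) | Arm 1 (two 1000/62.5 ER) |
|---|---|---|
| One tablet is regular amoxicillin/clavulanate | True | Not true if 'regular' means 875/125 |
| The other is a different formulation, or inactive | True (inactive) | Not true: same formulation, and active |

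The second row does not depend on how 'regular' is read. A second manufacturer of the same 1000/62.5 ER tablet changes its look, not its formulation.

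**Step 3. What the patient may see.** Two things decide the pattern within a dose: whether two manufacturers are found for arm 1, and whether the placebo resembles the 875/125 tablet. The available text settles neither.

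| Arm 1 pair | Arm 2 pair | Pattern differs by arm? |
|---|---|---|
| Unlike (sourcing succeeds) | Unlike | No |
| Alike (sourcing fails) | Unlike | Yes |
| Unlike (sourcing succeeds) | Alike | Yes |
| Alike (sourcing fails) | Alike | No |

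The plan is thus open to two combinations in which the pattern depends on the arm. The second row is the one that a sourcing failure could produce. In the last row there is no difference in pattern, but item 11 is still untrue of arm 1.

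**Step 4. The cost allowance.** Costs item 1a gives $10,854 for the high-dose drug and a ceiling of $12,000:

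- 12,000 − 10,854 = $1,146 in total.
- 1,146 / 150 = $7.64 per high-dose patient.
- 1,146 / 10,854 = 10.6%.

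The itemised lines sum to 10,854 + 1,050 + 750 + 300 + 6,000 + 2,000 + 2,000 + 30,000 + 60 + 150 = $53,164, or $54,310 with the ceiling. Without the optional research assistant ($8,000) they give $45,164 and $46,310. The stated overall cost is $44,550, below all four. The allowance is foreseen in one line, but the total does not demonstrably cover it.

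**The case against.** The strongest reply is that the cue is weaker than it looks. Item 11 speaks of what the tablets contain. On appearance it is only conditional, and it never says that the two will look different. An identical pair fits an active tablet with a matched placebo, so a high-dose patient holding one has no clear ground for inferring the high dose and might infer the opposite. The placebo's appearance is not described (Costs item 1c shows that even its price was still being sought), so it is not shown that arm 2 pairs would look unlike. A patient also sees only his or her own pair. All of this stands, and it limits the point to a possible cue.

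It can also be said that 'regular' may simply mean ordinary. That helps with the first half of the statement but not with the second.

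The plan does take other steps to protect or check the blind: the pharmacist holds the allocation list, the dose is left out of the health record entry, and the day-10 guess is analysed against outcome. The first two do not bear on what the patient sees in the bottle, and the third comes too late.

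Finally, the Enrollment Script and consent form may be worded correctly. That is possible, and it is why the absence of a requirement or fallback is asserted only for the available text. A correct script would, however, conflict with item 11, so reconciliation is needed either way.

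**Conclusion.** The point holds as a documented inconsistency together with a safeguard that is not firm. Item 11 misdescribes the high-dose arm, which follows from the tablet strengths alone. In the available text, the only provision for that arm's appearance is an intention under Costs.

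A reader might go further and infer that high-dose patients will be unblinded, or that the primary result will be biased in favour of high dose. The documents do not support that. It would require that sourcing fails, that the placebo looks unlike the 875/125 tablet, that patients notice their identical pair and read it as high dose, and that their ratings move. No link in this chain has a probability in the documents, and neither the size nor the direction of any bias can be computed. False-positive rates worked out under an assumed rating shift would apply to any trial of this size and response rate, so they add no weight here.

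The point is still worth correcting before bottles are filled, because the primary endpoint is a subjective self-rating within three days and the correction is small. Confidence is moderate, mainly because the script and consent form could not be read.

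**What to change.** 1. **Reconcile item 11 with the Treatment arms section**, using one statement that is true of both arms. For example: each dose is two tablets, which may or may not look alike; at least one contains amoxicillin/clavulanate, and the other contains amoxicillin/clavulanate or an inactive ingredient. Check the Enrollment Script and consent form against it. This is a wording change only.

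2. **Move the appearance plan from Costs into the Procedure**, as a condition to be met before any bottle is filled: the two tablets of a dose are alike in both arms or unlike in both arms, whether by sourcing or by masking. This also requires the placebo's appearance to be specified.

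The first change makes the statement true but does not protect the blind if the pattern differs by arm; the second does that. The second carries a modest sourcing or masking cost and may cause a short delay if a second manufacturer is not found. The $1,146 foreseen under Costs item 1a is a guide to the sourcing route only. Other masking is not priced, and the overall budget should be re-added before relying on that allowance. Neither change alters a dose or a clinical rule.
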